8.4 Exhaled Breath Sampling

All Donors and secondarily influenza-infected Recipients will be asked to provide exhaled breath samples using the Gesundheit-II cone collector (and/or next generation iEBA sampler, when available). The participant will be instructed to sit inside a tented apparatus containing the cone collector. The participant's face will be placed near the wide part of a metal funnel (the cone-shaped sampling instrument) or newer transparent cone with conductive coating. Breath samples are collected through the instrument's gentle and controlled suction of air into the narrow part of the funnel and into the instrument's collection system. Samples will be collected for a 30-minute period with the participant breathing normally. Participants will also be instructed to perform several prescribed maneuvers. For example, at 5-minute intervals over 25 minutes the participant will be asked to recite standard text (e.g., the alphabet), talk loudly, shout, or sing. The iEBA sampling instrument is able to fractionate different sized particles and these fractionated samples can be assayed by quantitative viral culture, serial passaged for detection of low concentrations of virus, and RTqPCR. Within the EMIT-2 program, a newer iEBA collection instrument (e.g., Gesundheit-III) will be developed and is intended to be a supplement and replace the Gesundheit-II over the course of the 5-year grant. It is anticipated that newer instruments may replace the tent with a hood resembling a loose-fitting powered air-purifying respirator. It is also anticipated that some shorter duration (5-15 minute) samples may be collected using a spirometry

mouthpiece and nose clip while the participant breathes slowly and deeply or coughs, and that a few deep breaths while vocalizing through a spirometry mouthpiece may also be collected.

8.5 Environmental and Personal Sampling

Sampling will also be conducted throughout the exposure room and may also be performed in other areas where CHIVITT participants reside, including the common rooms, bathroom, showers, and bedrooms. Surface swabs of common contact surfaces (fomites) will be collected and evaluated for the presence of influenza virus by PCR and culture.

Within the EMIT-2 program's Advanced Bioaerosol Technology Core (ABTC), a novel ambient sampling system will be developed. The following description of the device provides the aspirational goal of the device. The device will use a 3-stage water-based condensational growth technology to enlarge airborne nanoparticles as small as 10 nm to micrometer size under moderate temperatures without using steam injection or heat. The water condensation technique encapsulates each airborne particle within a water shell that enables direct impaction of these particles onto solid or liquid surfaces for delivery to in vitro assays. Gentle impaction will be achieved by delivering the particle-containing flow through multiple nozzles. Because condensation is achieved at moderate temperature, and impaction velocities are optimized to minimize membrane damage, this technology retains high infectivity of airborne pathogens. Significantly, the technology will allow for each system to be tuned for collection into buffer for bulk analysis of total viral RNA or into culture media cell inoculation by live virus; onto hydrogel membranes for efficient collection and culture of viable virus; or into an oil phase to form water emulsions enabling single aerosol particle analysis.

Environmental and personal samples will also be collected using NIOSH BC251 cascade samplers – the current standard method for bioaerosol collection. The NIOSH BC251 is a two-stage dry cyclone employing two 1.5 mL microcentrifuge Eppendorf tubes screwed into a small metal base with a backup filter as a final third stage. Coupled with a small 3.5 liter/minute personal air sampling pump it has been extensively used for area as well as personal sampling to monitor viral aerosol exposures of healthcare workers. Personal air samples may be collected from Recipients by providing them with a waist belt mounted personal air sampling pump (weight, approximately 22 oz) and attached shoulder strap for mounting the BC251 (<6 oz) in their breathing zone.

8.6 Data for Secondary Research

Data from this study may be used for secondary research. Only individual subject data that has been coded will be made available for secondary research. The Statistical Analysis Plan (SAP) and Analytic Code will also be made available. Data will be available immediately following publication, with no end date. De-identified data may be used for secondary research without further consent of the subject. Any coded or identifiable data used for secondary research may occur if the subject agreed to use by signing this study consent form and has not withdrawn their consent.

9 OUTCOMES AND DATA ANALYSIS

9.1 Primary Outcome Measure – Attack Rate of Influenza

The SAR of influenza infection will consist of virological confirmation, symptomatic infection, or serological evidence of an influenza infection.

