5 CHIVITT OBJECTIVES

Table: Objectives and Endpoints (Outcome Measures)

Objectives	Endpoints (Outcome Measures)
Primary	

 • To determine the relative contribution of the various modes of transmission 	
 • SAR of influenza infection will be determined through virological confirmation, symptomatic infection, or serological evidence
Secondary	

 • To measure influenza viral parameters in Donors and Recipients • To measure influenza illness parameters in Donors and Recipients to assess the impact of aerosol exposure to influenza on disease severity • To evaluate the role of serologic antibody levels on influenza transmission, susceptibility, and immunologic response to infection 	
 • Incidence, duration, and quantity of virus shedding in donors and recipients • Disease severity parameters in donors and recipients • HAI, NI, and FRNT titers, HA/NA anti-stalk ELISA, and ADCC reporter assays. • Measurement and modeling of aerosol size, virus number per aerosol particle,

• To estimate the infective dose of influenza virus	deposition and environmental dispersion characteristics, and rate of shedding
Exploratory	

 To evaluate the role of mucosal antibody and cellular immunity in transmission and susceptibility. To characterize the quantum of airborne influenza infection and extend models of aerosol inhalation risk from well-mixed to non-well mixed conditions and the personal breathing zone. 	
 Potential assays include IgA in nasal secretions and collection and analysis of cellular immune markers. Exhaled breath viral loads and ambient viral concentrations, environmental parameters, video analysis of individual movement and interpersonal proximity and behaviors.

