6.1 General Outline of Activities During Each CHIVITT Cohort

The CHIVITT is to be conducted as a randomized, open, controlled study. Recipient participants for each cohort will enter the study hotel quarantine facility and be housed in individual hotel rooms. After a two-day run-in period to ensure that Recipients are free of preexisting respiratory infections *Exposure Events* will be held in a specially prepared event room.

Recipient participants of each cohort will be randomized to an intervention group or no intervention (Control Recipients, CR). Before entering their first *Exposure Event* each Intervention Recipients (IR) will be trained on how to comply with the intervention. IRs will be required to wear a lightweight plastic face shield, comply with hand hygiene (i.e., using a hand sanitization product every 15 minutes, plus periodic hand washing with soap and water), and avoid face touching during each planned *exposure event*. The face shield may only be removed after leaving the exposure room to go to the bathroom, for other short comfort breaks, and at mealtimes. In these instances, hand hygiene will be used after removing or replacing the face shield; and Donors will not be present. Hand washing with soap and water will be required before meals. IR will be separated from Donors by more than 6 feet during meals. The exposure room will be supervised by a trained member of the study staff who will monitor to ensure that Intervention Recipients wear the face shield continuously, are separated from Donors at meals, and do not touch their faces. Small sticks (e.g., coffee stirrers) will be provided to allow IRs to scratch their faces.

Exposure events are to occur as controlled (prescribed) activities within the exposure room. Exposure events will extend for up to 15 hours per day when Donors are available and able to participate (e.g., 15 hours 8am to 11pm). Each Recipient will participate in up to 60 hours of *Exposure Events* (e.g., 4 days at 15 hours/day) which may be spread over up to 9 or 10 days. During each *Exposure Event* multiple 1-3 hour group activities will be planned and supervised by trained members of the study staff. The group activities are intended to be entertaining and may consist of participating in a card game, board game, foosball game, karaoke, or other group activity which facilitates crowding, loud talking, etc. for potential influenza transmission.

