Should a recipient become laboratory-confirmed influenza infected (a countable SAR) and have accompanying symptoms during the CHIVITT, then the Recipient may be allowed to continue in the CHIVITT as a Donor. In order to accept the Recipient into the Donor status, the Donor informed consent form must be reviewed and signed by the participant. Recipients who are a countable SAR and do not want to continue in the CHIVITT may be safely discharged, contingent upon the absence of sufficient illness which may require treatment of influenza ([section 6.6](#)). However, once the 2 weeks have transpired, and if they have not become influenza infected, they will be allowed to end their participation in the CHIVITT. Recipients will also be allowed to withdraw from the study early, for their own personal reasons (see [section 6.7](#)).

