8.1.3 Daily Assessments

- Vital signs (including SpO₂, HR, RR, BP, and oral temperature) will be obtained at least twice daily (intended to be at least once in morning and once in afternoon). After the first two days, vital signs will be collected once a day until after exposure to a Donor or at PI discretion.
- A targeted physical examination may be performed, as directed by the medical history, medications, and vital signs assessment. An absence of significant past medical history, concomitant prescription medications, and abnormalities in vital signs will not require a physical examination.
- Once daily collection of a respiratory sample for viral quantitation and performance of a combined influenza and SARS-CoV-2 test (e.g., BioFire Respiratory Virus panel). After the

first two days of negative tests these daily assessments may be paused until after exposure to the first Donor.

- Twice daily completion of a Modified Jackson Score, Investigator Assessment Tool ([Appendix C](#)).
- Once daily completion of a self-reported Symptom Diary, FLU-PRO Survey Instrument and Validation Diary ([Appendix B](#)).
- Additional nasal swab and a saliva sample for research tests. However, these two samples will not be collected between the period after the incubation and before the first donor arrives.
- For Donors, Exhaled breath sampling

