9.1.1 Viral Confirmation of Influenza Infection

BioFire Respiratory Panel. This CLIA-approved, commercially available molecular diagnostic test will be the primary means for determining influenza infection. The test result will be used for the day-to-day management and decision-making process for the care of study participants.

Cepheid 4-Plex. This CLIA-waived, commercially available molecular diagnostic test (which runs the Xpert® Xpress SARS-CoV-2/Flu/RSV assay) can be a satisfactory alternative means for determining influenza infection from the BioFire Respiratory Panel.

Qualitative RT-PCR. This research diagnostic test will be used as a secondary means for determining influenza infection. The test result may not be available for day-to-day decisions and the test may be performed in batched analysis.

Quantitative RT-PCR. This research diagnostic test will be used as another secondary means for the characterization of influenza infection. Peak viral shedding will be calculated for each subject as the maximum shedding during their CHIVITT participation period. Total viral shedding will be calculated with an area under the curve (AUC) with study day on the x-axis and shedding on the y-axis. The test result may not be available for day-to-day decisions and the test may be performed in batched analysis.

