9.1.2 Symptomatic Influenza Infection

Modified Jackson Instrument score. ([Appendix C](#)) Symptomatic influenza infection for determining AR will be assessed using a Modified Jackson score collected by study staff twice a day (approximately 8 AM and after 3 PM) from the time of admission until the time of discharge. The Modified Jackson score will be calculated after evaluation of vital signs, laboratory results, and the Modified Jackson score across multiple days.

FluPro® participant reported tool. ([Appendix B](#)) A previously validated, patient-reported outcome (PRO) measure to standardize the assessment of influenza symptoms in clinical research (i.e., FLU-PRO Survey Instrument and Validation Diary) will be completed by subjects once a day (after 3:00 PM) from the time of admission through discharge. The investigators will review the FLU-PRO and Validation Diary responses each day.

Fever. A febrile illness, with or without accompanying symptoms, will be defined as an occurrence of an oral temperature of $\geq 100.2^{\circ}\text{F}$ ($\geq 37.9^{\circ}\text{C}$). *Note: a qualifying temperature of $100.2^{\circ}\text{F}-100.5^{\circ}\text{F}$ does not constitute a gradable toxicity (see [Appendix A](#)).* Elevated temperatures must be confirmed with a repeat measurement within 5-60 minutes.

Clinical Findings of Respiratory Tract Infection. At least once daily, the study physician will perform at least a limited physical examination of the head, neck, and lungs; a directed or more detailed physical examination may be performed at the discretion of the study physician for any reason. Physical examination findings which would be consistent with an influenza infection will include:

- Nasal discharge
- Otitis
- Sinus tenderness
- Pharyngitis
- New wheeze, rales, rhonchi, or other lower tract signs

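### Symptomatic infection without laboratory evidence can count as a primary event in an open trial; Sections 5 and 9.1 should require laboratory confirmation

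*Protocol*

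**What the plan says.** Protocol Section 9.1 states: "The SAR of influenza infection will consist of virological confirmation, symptomatic infection, or serological evidence of an influenza infection". The objectives table in Section 5 has the same rule: "SAR of influenza infection will be determined through virological confirmation, symptomatic infection, or serological evidence". Both use a plain alternative, so each route suffices by itself.

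Section 9.1.2 confirms that the symptom route is meant for case counting, since it assigns the Modified Jackson score to the determination of the attack rate. Under the same heading it lists FLU-PRO, a confirmed temperature of at least 100.2°F whether or not symptoms accompany it, and examination signs, introduced by "Physical examination findings which would be consistent with an influenza infection will include" (nasal discharge, otitis, sinus tenderness, pharyngitis, lower tract signs). It does not make a positive influenza test a condition.

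Elsewhere the emphasis is on the laboratory. Section 6.4 reads: "Should a recipient become laboratory-confirmed influenza infected (a countable SAR) and have accompanying symptoms during the CHIVITT". Section 9.1.1 says of the BioFire panel: "This CLIA-approved, commercially available molecular diagnostic test will be the primary means for determining influenza infection". Donors must have laboratory confirmation as well as illness (Section 3.2, inclusion criteria 4 and 5).

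On blinding, Section 6.1 states: "The CHIVITT is to be conducted as a randomized, open, controlled study".

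**The concern.** The symptom route is the part of the primary endpoint that depends on subjective report. The Jackson items in Appendix C are symptoms as the participant reports them, collected by staff, and FLU-PRO is self-completed. Intervention Recipients wear a face shield and sanitise their hands every 15 minutes, so participants and staff know the assignment.

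Two harms can follow. If illness other than influenza is counted at the same rate in both groups, both contrasts are diluted and power is lost. If knowledge of assignment shifts reporting, the endpoint can show a difference that transmission did not cause.

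The wording also reaches beyond the analysis. Section 6.6 ties the start of antiviral treatment to any criterion that satisfies the primary outcome, so an unclear event definition carries over into that section.

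**Working it through.** **Inputs from Section 9.2.** Expected SAR 25%. Air hygiene: 79% reduction, so 0.25 × 0.21 = 5.25%, with 54 in the intervention group. Hand hygiene and face shield: 76% reduction, so 0.25 × 0.24 = 6.0%, with 63 in the intervention group. One-sided test, alpha 5%, stated power 84% for each. **Assumed:** a control group of equal size, which the protocol does not state.

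**Reproducing the stated power.** With continuity correction, power = Φ[(p1 − p2 − 1/n − 1.645·SE0)/SE1], where SE0 = √(2p̄(1−p̄)/n) and SE1 = √((p1(1−p1) + p2(1−p2))/n).

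- n = 54: (0.1975 − 0.0185 − 1.645 × 0.0690)/0.0663 = 0.99, power 83.9%.
- n = 63: (0.1900 − 0.0159 − 1.645 × 0.0645)/0.0622 = 1.09, power 86.3%.

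The first matches 84% and the second is 2.3 points above it. An uncorrected two-sided z test gives 82.7% and 84.7%. The choice of formula does not affect the point made here.

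**Equal false-case rate.** Let f be the probability that a Recipient without influenza is counted on symptoms. The documents give no value, so 5%, 10% and 20% are assumptions. Observed rate = p + (1 − p)f.

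| f | Control | Air hygiene | Apparent reduction | Power, n = 54 | Shield and hands | Apparent reduction | Power, n = 63 |
|---|---|---|---|---|---|---|---|
| 0 | 25.0% | 5.25% | 79% | 84% | 6.0% | 76% | 86% |
| 5% | 28.75% | 10.0% | 65% | 72% | 10.7% | 63% | 76% |
| 10% | 32.5% | 14.7% | 55% | 62% | 15.4% | 53% | 66% |
| 20% | 40.0% | 24.2% | 40% | 46% | 24.8% | 38% | 50% |

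Power is one-sided with continuity correction. The two-sided z test shows the same pattern: 70%, 59% and 42% at n = 54, and 73%, 62% and 45% at n = 63.

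**Unequal rate, no true effect.** Take f = 10% in controls and 5% in the intervention group (both assumed), with a true SAR of 25% in each.

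- Control: 0.25 + 0.75 × 0.10 = 32.5%.
- Intervention: 0.25 + 0.75 × 0.05 = 28.75%.
- Spurious reduction: 1 − 28.75/32.5 = 11.5%.
- Rejection by an uncorrected one-sided 5% z test at n = 63: (0.0375 − 1.645 × 0.0821)/0.0821 = −1.19, so 11.7%. At n = 54 it is 11.1%.

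A continuity-corrected test, being conservative, would reject less often.

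**The case against.** Several stronger readings are tempting, and the documents do not support them.

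- *Any single cold sign makes a case.* No section says so. Section 9.1.2 gives the attack-rate role to the Jackson score, calculated after looking at vital signs, laboratory results and scores over several days. The signs are described only as consistent with influenza. What stands is narrower: nothing in 9.1.2 excludes counting non-specific signs, and the mention of laboratory results is not a requirement of a positive influenza test.
- *The protocol has two primary endpoints.* Section 6.4 concerns a Recipient's move to Donor status and gives a sufficient condition for counting. It does not say that only such cases count, and it could not be the whole endpoint, because serology is batched and unavailable for daily decisions (Section 9.1.3). It is in tension with Sections 5 and 9.1, but it is not a rival definition.
- *Symptom-only cases are mostly false positives.* This is not shown. Discharge may come two days after the last exposure, with a home test only optional (Section 6.9). Serological confirmation is by HAI (Section 9.1.3), while Section 8.2 says that H3N2 viruses without HA activity need FRNT. Some unconfirmed cases could be true infections.

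There are safeguards: the admission panel, the two-day run-in, private rooms, daily testing after exposure, repeat temperature measurement and possible withdrawal for another virus. They should lower f, but none is a condition for counting a case.

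A Jackson cut-off may properly be left to the SAP, so its absence is not part of this point. A cut-off would not remove the alternative wording or bring in laboratory evidence.

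Section 8.1.3 says "An absence of significant past medical history, concomitant prescription medications, and abnormalities in vital signs will not require a physical examination", whereas 9.1.2 has the physician examine at least once daily. That conflict is real but separate, and it does not show that the endpoint is wrong.

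**Conclusion.** The point holds in this form. Sections 5 and 9.1 allow a primary event on symptoms without laboratory evidence, in an open trial and at odds with the emphasis of Sections 6.4 and 9.1.1. The protocol itself fixes this wording.

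The direction of the dilution from equal false cases does not depend on the rate chosen. Its size does: with 5% to 20% false cases in each group, power falls to between 72% and 46% for air hygiene and between 76% and 50% for the shield and hand-hygiene contrast. The bias example (11.5% spurious reduction, about 11–12% rejection) also rests on assumed rates. It applies most directly to the shield contrast, where assignment is visible. A larger proportionate bias would require an SAR below the protocol's own 25%.

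**What to change.** In Sections 5 and 9.1, count a primary event only with laboratory confirmation after first exposure: a positive BioFire, Cepheid or RT-PCR result, or a rise of at least 4-fold in paired sera. State explicitly what becomes of the seropositive criterion in Section 9.1.3 (titre of at least 40 at one month), which is now a further serological route. Report symptomatic laboratory-confirmed influenza as a secondary endpoint, and use Jackson, FLU-PRO, fever and examination findings as severity measures. A sensitivity analysis can keep the three-way composite.

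No new tests are needed: swabs and sera are already scheduled for every Recipient (Sections 8.1.1, 8.1.3 and 8.1.8). The small statistical cost is that a few true infections missed by both swab and serology would no longer count.

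More than the endpoint wording is involved. Because Section 6.6 ties antiviral timing to the primary-outcome criteria, Sections 5, 6.4, 6.6, 9.1 and 9.1.2 must be reconciled together, so that the change does not silently alter that clinical trigger. No clinical rule is proposed here.
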